10. TREATMENT OF PATIENTS

10.1. Treatments Administered

Using electromyography (EMG) or ultrasound guidance, each dose of study drug will be administered into the non-tendinous portion of the TA as a series of up to 4 equal-volume injections. The use of EMG or ultrasound guidance will ensure that viable muscle is present at the injection site. If the degree of atrophy or fibro-fatty infiltration poses administration challenges, injections of ACE-083 should be distributed approximately 2 cm apart into viable muscle. Injection site locations as well as measures to avoid adjacent nerves, blood vessels, and prevent intravascular injection are outlined in the IP Handling Guide.

The maximum absolute dose level and schedule, based on SRT review, is 250 mg/muscle administered bilaterally by injection into the left and right TA muscles every 3 weeks for up to 5 doses in Part 1 and up to 17 doses in Part 2.

For Part 2, ACE-083 or placebo (normal saline) will be administered blinded study drug every 3 weeks for approximately 6 months (9 doses). Patients who complete the double-blind treatment period will immediately roll over to open-label treatment with ACE-083, receiving the same dose of active drug, bilaterally in the TA muscle once every 3 weeks for approximately 6 months (8 doses).

The planned dose scheme for Part 1 and 2 is shown in Table 4.

Table 4:Cohort Schedule for Study A083-03

Part 1: N=U	o to 18 ((non-randomized, o	open-label, d	lose-escalation)
		(

Cohort	ACE-083 Dose per Muscle ^a	ACE-083 n
1	150 mg	6
2	TBD up to 200 mg ^b	6
3	TBD up to 250 mg ^b	6

Part 2: N= Up to 40 (6-month, randomized, double-blind, placebo-controlled, with 6-month open-label extension)

	6-month double contro	6-month open-label extension	
ACE-083 Dose per Muscle ^a	ACE-083 n	Placebo n	ACE-083 n
TBD up to 250 mg ^b	20	20	40

^a Administered bilaterally by injection into the tibialis anterior muscle once every 3 weeks

^b Dose level to be based on recommendations from the SRT

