14.4. Interim Analysis

For Part 1, periodic reviews of the available safety and tolerability will be done to assist dose escalation decisions. For Part 2, no interim analyses are planned.

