## 4. STATISTICAL METHODS

### 4.1. General Method

#### 4.1.1. Sample Size Determination

There was no formal sample size calculation for Part 1. Six patients in each cohort will provide sufficient data to evaluate safety and a preliminary assessment of changes in muscle volume and muscle strength.

The sample size calculation for Part 2 is based upon the percent change from baseline in total muscle volume of the injected TA muscle 3 weeks after the last dose. A 10% difference between ACE-083-treated and placebo groups in the percent change in total muscle volume from baseline is considered to be clinically meaningful. The standard deviation (SD) is assumed to be approximately 10% for each group, based on preliminary MRI data for the ACE-083-treated side from the initial TA cohort in Part 1 of the Phase 2 study in FSHD patients.

Assuming a 2-sided type I error rate of 0.10, a 10% difference in percent change from baseline between ACE-083-treated and placebo groups in total muscle volume, a standard deviation of 10% for each group, and a 1:1 randomization, 90% power is achieved with a total sample size of 36 (18 active, 18 placebo), based on a standard t-test.

In addition, this sample size also provides 90% power to detect a 10% difference in 6-minute walk test distance, based on a similar estimated SD of 10% (based off of available data from Part 1 of the Phase 2 study in FSHD patients as well as data from Part 1 of this study, 3-weeks post last dose) and a 2-sided type 1 error rate of 0.10.

In order to account for dropouts (up to 10%), 40 patients will be randomized to study treatment for each muscle (20 active, 20 placebo) to ensure that at least 18 patients per treatment group complete the double-blind treatment period.

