## 4.2. Analysis Population

The analysis populations include the following:

- Full Analysis Set: Part 1 – All patients enrolled in the study receiving at least one dose of ACE-083. Part 2 – All patients randomized who have received at least one dose of study drug (includes placebo);
- Safety Set: All patients enrolled/randomized in the study who have received at least one dose of study drug (includes placebo);
- Per Protocol Set: All patients enrolled/randomized in the study who have received at least one dose of study drug (includes placebo) with no data or study procedural related issues that would otherwise impact the interpretability of the efficacy and/or pharmacodynamic data.

Such issues include but are not necessarily limited to:

- Patients who discontinue the study prior to the Dose 3 Day 43 visit; these patients may have been replaced per protocol
- Patients whose Day 1 MRI or Day 190 MRI was done 7 or more days following study drug administration
- Patients who did not receive the full study drug administration planned per protocol at all injection sites on any or both sides (right or left) for 2 or more consecutive visits for reasons other than dose reductions for the safety of the patient or feasibility concern (i.e., the site intended to administer the full dose but was unable).

- Patients whose Screening cumulative distance walked at 6 minutes is greater than 500 meters or less than 150 meters.

A review of the patient data will be performed and a list of patients to be excluded from the Per Protocol Set along with the reason for exclusion will be completed before the data is locked and unblinded.

Statistical analyses of efficacy and pharmacodynamics data will be performed on the Per Protocol Set (primary analysis population) and the Full Analysis Set (secondary analysis population). Analyses of safety data will be performed on the Safety Set. Should the statistical analysis populations be identical (e.g., Full Analysis Set = Per Protocol Set), statistical analyses will not be duplicated or repeated.

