### **4.8.2.2. Part 2**

#### **4.8.2.2.1. Double-Blind Period**

##### **MRI: Total Muscle Volume (TMV)**

Individual total muscle volume data will be listed.

Descriptive statistics will be provided by treatment group and scheduled time for raw data and changes from baseline (absolute and percent change) for each side [left and right]. The average absolute change and average of the percent change for the left and right sides will also be provided.

The primary pharmacodynamic analysis will consist of an ANCOVA in order to assess the effect of ACE-083 on the Day 190 average percent change from baseline for the left and right sides. Covariates to be included into the model are TREATMENT, BASELINE, and CMT-TYPE where:

- TREATMENT represents the treatment group (ACE-083 or placebo)
- BASELINE represents the baseline total muscle volume (average of left and right sides)
- CMT-TYPE refers to the type of CMT (e.g. CMT1 or CMTX)

The effect of ACE-083 versus placebo will be estimated using the ANCOVA model described above and tested using a 0.1 significance level (2-sided). The least-square mean estimate along

with the corresponding 90% confidence interval will be provided. In addition, the 95% confidence interval will also be provided.

If the Day 190 TMV has no missing data, then the above ANCOVA model will be used for analysis. If missing data is present, a standard multiple imputation with the above ANCOVA model will be used for analysis as described in [Section 4.11.1](#).

A mixed model repeated measures (MMRM) analysis will be performed to assess the sensitivity to the ANCOVA analysis described above. An unstructured covariance structure will be used to model the within-patient covariance across visits. Other covariance structures will be considered if the unstructured covariance fails. The covariates to be included consist of all of the covariates described above for the ANCOVA with the addition of the following additional covariates: VISIT where VISIT represents the scheduled visit day post first dose of MRI assessment and TREATMENT\*VISIT.

Similar to what was described for the ANCOVA analysis above, if missing data is present, a standard multiple imputation with the above MMRM model will be used for analysis as described in Section 4.11.1.

The statistical analyses described above will be done on the Per Protocol Set and will be considered primary. The analyses described above will also be repeated for the Full Analysis Set.

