#### 4.8.2.2.3. Open-Label vs. Double-Blind Placebo-Controlled Period

##### **MRI: TMV**

The effect of ACE-083 administered during the open-label extension compared to the treatment administered in the double-blind placebo-controlled phase will be examined for those receiving ACE-083 during the double-blind phase and separately for those receiving placebo during the double-blind phase by comparing the average percent change (left and right side) observed between Day 190 and pre-first treatment baseline (1st 6 months) and Day 358 versus Day 190 (2nd 6 months) using an ANCOVA model.

Covariates to be included into the model are SEQUENCE, CMT-TYPE, and BASELINE where:

- SEQUENCE represents the treatment sequence from double blind to open-label (ACE-083 → ACE-083 or Placebo → ACE-083)
- CMT-TYPE refers to the type of CMT (e.g. CMT1 or CMTX)
- BASELINE represents the baseline TMV from the double-blind period

Least squares estimates of the SEQUENCE effect and 90% confidence intervals will be provided.

If the Day 358 and/or Day 190 assessments have no missing data, then the above ANCOVA model will be used for analysis. If missing data is present, a standard multiple imputation with the above ANCOVA model will be used for analysis as described in [Section 4.11.1](#).

The statistical analysis described above will be done on the Per Protocol Set and will be considered primary. The analyses described above will also be repeated for the Full Analysis Set.

In addition, a line graph of the mean ± SEM of the percent change from baseline will be provided by sequence for each scheduled time.

Additional analyses may be performed as appropriate.

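### The Per Protocol Set dosing exclusion names no dose range, so incomplete open-label dosing after Day 190 can remove a valid Day 190 value from the primary muscle volume analysis

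*SAP*

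**What the plan says.** SAP 4.2 defines one Per Protocol Set and makes it the primary population for efficacy and pharmacodynamic data. It lists four kinds of problem that take a patient out. Three are tied to a named visit: discontinuation before the Day 43 visit, a late Day 1 or Day 190 MRI, and a Screening six-minute walk distance outside 150 to 500 metres. The fourth concerns dosing. A patient is removed if the full planned administration was not given at every injection site, on one side or both, "for 2 or more consecutive visits for reasons other than dose reductions for the safety of the patient or feasibility concern". No dose number, visit or study period is attached to it.

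Protocol 10.1 sets the planned dosing at "up to 5 doses in Part 1 and up to 17 doses in Part 2". In Part 2 these are nine double-blind doses and eight open-label doses. Dose 10, at Day 190, is the first open-label dose. The schedule of events in both documents places study procedures before dosing at each visit.

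The set is used twice in the muscle volume analyses. For the Day 190 ANCOVA, SAP 4.8.2.2.1 says: "The statistical analyses described above will be done on the Per Protocol Set and will be considered primary". For the comparison of the second six months with the first, SAP 4.8.2.2.3 says: "The statistical analysis described above will be done on the Per Protocol Set and will be considered primary". Both are repeated on the Full Analysis Set, which SAP 4.2 ranks as secondary.

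The list of excluded patients is to be completed before lock and unblinding. Protocol 14.4 adds: "For Part 2, no interim analyses are planned". Neither document describes a separate lock at Day 190.

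**The concern.** Dose 10 and everything after it is scheduled to follow the Day 190 measurement. A rule that looks at those doses makes membership of the primary randomised comparison depend on events after the endpoint, at a time when placebo patients have moved to active drug. Valid Day 190 values would leave the primary analysis for a reason that has nothing to do with how they were obtained. If completing open-label injections is related to how a patient fared in the first six months, and differently so in the two treatment sequences, the primary estimate would also be exposed to selection.

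**Working it through.** **1. Does any text confine the rule to Doses 1 to 9?** None was found. Elsewhere the SAP names the period when it means one: the ADA and activity-level subgroups in 4.9 refer to the Part 2 double-blind period, and the dose counts in 4.6.1 are split by period. The dosing criterion has no such limit. Because the set also serves the Day 358 comparisons, a programmer has a reason to count Doses 10 to 17.

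**2. Which dose pairs can trigger it?** Seventeen doses form 16 consecutive pairs. Eight lie within Doses 1 to 9, one straddles Doses 9 and 10, and seven lie within Doses 10 to 17. So 8 of the 16 pairs include a dose given at or after the Day 190 visit. This counts patterns; it is not a risk. Part 1 is not affected, since its five doses all precede the Day 106 assessment.

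**3. Can those doses affect the Day 190 value?** By schedule, no. There is one narrow exception: SAP 4.1.5 accepts a Day 190 assessment made up to 7 days after Dose 10. Late MRIs already have their own criterion in SAP 4.2.

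**4. The plan's own power figure.** The inputs are in SAP 4.1.1. The target δ is "a 10% difference in percent change from baseline between ACE-083-treated and placebo groups in total muscle volume", that is, 10 points. The SD σ is 10 points in each arm, allocation is equal, and the test is two-sided at 0.10. For a two-sample t-test, the noncentrality is λ = δ / (σ√(1/n₁ + 1/n₂)), with n₁ + n₂ − 2 degrees of freedom.

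- At 18 per arm, λ = 10 / (10 × √(2/18)) = 3.00 on 34 degrees of freedom, and power is 0.9023. The stated 90% with 36 patients reproduces.
- 36 / 0.90 = 40, so the number randomised also reproduces.

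**5. Power if evaluable patients are lost.** The number lost is an assumption, because the documents give no open-label non-dosing rate.

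| Lost from 18 | Both arms | One arm only |
|---|---|---|
| 0 | 0.9023 | 0.9023 |
| 1 | 0.8865 | 0.8944 |
| 2 | 0.8684 | 0.8855 |
| 3 | 0.8477 | 0.8754 |
| 4 | 0.8241 | 0.8637 |

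Starting at 18 assumes the 10% dropout allowance is already used. With all 20 per arm evaluable, power is 0.9279, and losing 2 per arm only brings it back to 0.9023.

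**6. Selection (illustration only).** If k of 18 patients in one arm are removed and their mean lies s points below that arm's mean, the arm mean rises by k × s / (18 − k). With s assumed at 5 to 10 points:

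- k = 2 gives 10/16 to 20/16, or about 0.6 to 1.3 points.
- k = 3 gives 15/15 to 30/15, or 1.0 to 2.0 points.

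The target difference is 10 points. If s is zero there is no shift. If both arms shift equally, the treatment difference does not change.

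**The case against.** The best reply is that the gap is one of silence. The criteria are offered as examples of problems that harm the interpretability of the data, and incomplete open-label dosing does not harm a Day 190 MRI. A blinded review with a recorded reason for each exclusion could confine the rule sensibly. This has force, but it does not settle the matter. The dosing criterion is itself listed as such a problem, the set is a single patient-level flag, and incomplete dosing that matters at Day 358 would take the patient out at Day 190 too. The review guards against manipulation; it does not supply the missing rule.

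Second, the Full Analysis Set repeat retains every such patient, and a divergence between the two analyses would be visible. That stands. The values are lost to the primary analysis, not to the trial.

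Third, the timing of the exclusion list is not dated. That open-label records will be to hand when it is drawn up is an inference from the absence of an interim analysis or a Day 190 lock.

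Fourth, one might picture a patient who skips Doses 12 and 13 and then resumes. That would leave Day 211 to Day 274, or nine weeks, between doses. Protocol 10.1.1, written for adverse-event pauses, ends treatment if dosing has not resumed within six weeks, and the visit windows allow for delayed doses. The documents do not show this to be a likely route. Partial administration at two consecutive open-label visits is enough to trigger the rule and does not depend on that example.

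A reader might also infer that the criterion removes everyone who stops treatment after Day 43, leaving little for the planned imputation to act on. The documents do not support this. The wording concerns administration at injection sites at visits, discontinuation has its own Day 43 criterion, and multiple imputation is planned for the same Per Protocol analysis. A reading that makes the neighbouring criterion redundant is unlikely to be the intended one.

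**Conclusion.** The point holds as a defect in the definition of the primary analysis set. As written, incomplete administration at two consecutive open-label visits, outside the safety and feasibility exemptions, removes a valid Day 190 value from the primary comparison. Nothing in either document limits the rule to Doses 1 to 9.

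Its size is modest and cannot be fixed from the documents. If the dropout allowance is used up and 2 or 3 further patients per arm are lost, power falls from 90.2% to about 87% or 85% on the plan's own t-test assumptions. Bias is possible but not demonstrated: it needs open-label dosing to be related to response and not to cancel between arms. The 8-in-16 pair count should not be read as the share of patients at risk. The change is worth making because it keeps post-endpoint behaviour out of the primary randomised comparison at almost no cost.

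**What to change.** In SAP 4.2, state that for Day 190 (double-blind) analyses the dosing exclusion considers Doses 1 to 9 only, and that dosing from Dose 10 onward is not considered. Define a separate per-protocol flag that applies the same criterion over Doses 1 to 17, and use it for the open-label versus double-blind analyses in SAP 4.7.2.2.3 and 4.8.2.2.3.

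The change should stop there. Counting only visits that the patient attended would keep someone who skipped several double-blind doses. Expressly retaining every later discontinuer would be a choice of estimand, not a clarification.

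The cost is one or two sentences and one more population flag in programming. No new data, dosing change or protocol amendment is needed. The downside is two Part 2 per-protocol flags instead of one, so each table must say which it uses.

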8. STUDY POPULATION

8.1. Inclusion Criteria

Patients are eligible to be included in the study only if they meet all of the following criteria at screening:

Inclusion Criteria:

- 1. Age ≥ 18 years
- 2. Diagnosis of CMT1 or CMTX confirmed by:
 - a. Clinical presentation and electrodiagnostics
 - b. Genetically confirmed CMT1 or CMTX (Appendix 3) for the patient or first-degree relative
- 3. Part 1:
 - a. Six-minute walk distance (6MWD) of at least 150 meters (without a brace or walker)
 - b. Independent ambulation for at least 10 meters, without a brace
 - c. Left and right ankle plantar flexion MRC grade 4+ to 5, inclusive

Part 2:

- a. $6MWD \ge 150$ and ≤ 500 meters (without a brace or walker); a maximum of 20% of enrolled patients with $6MWD \ge 450$ meters will be included
- b. Left and right ankle plantar flexion MRC grade 4- to 5, inclusive
- 4. Left and right ankle dorsiflexion Medical Research Council (MRC) manual muscle testing (MMT) grade 3 to 4+ inclusive (Appendix 4). No more than 12 of the 40 subjects may have a grade of 3 or 3+ on one or both sides.
- 5. Females of childbearing potential (defined as sexually mature women who have not undergone hysterectomy or bilateral oophorectomy, or are not naturally postmenopausal ≥ 24 consecutive months) must have negative urine pregnancy test prior to enrollment and use highly effective birth control methods (abstinence, oral contraceptives, barrier method with spermicide, or surgical sterilization) during study participation and for 8 weeks following the last dose of ACE-083. Hormonal birth control use must be stable for at least 14 days prior to Day 1. Males must agree to use a condom during any sexual contact with females of childbearing potential while participating in the study and for 8 weeks following the last dose of ACE-083, even if he has undergone a successful vasectomy. Patients must be counseled concerning measures to be used to prevent pregnancy prior to the first dose of ACE-083.
- 6. Ability to adhere to the study visit schedule/procedures, and to understand and comply with protocol requirements
- 7. Signed written informed consent

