14.1. Analysis Populations

Full Analysis Set: Part 1: All patients enrolled in the study and have received at least one dose of study drug; Part 2: All patients randomized in the study

Safety Population: All patients enrolled/randomized in the study who have received at least one dose of study drug (including placebo)

Per Protocol Set: All patients enrolled/randomized in the study, who have received at least one dose of study drug (including placebo) with no CSR-reportable protocol violations and at least one post-baseline MRI evaluation

Pharmacokinetic Population: All patients who have received at least one dose of study drug and have sufficient PK samples collected and assayed for PK analysis

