## 5. MODIFICATIONS FROM THE STATISTICAL SECTION OF THE PROTOCOL

The following modifications from the statistical section of the protocol have been implemented in the statistical analysis plan:

- For statistical analyses where confidence intervals for the least-squares mean are provided, the 95% confidence interval will be provided in addition to the 90% confidence interval.
- The “Safety Population” is now called the “Safety Set”.
- The “Per Protocol Set” definition was redefined to be what is listed in this document..
- The last observation carried forward approach is not being performed in the statistical analyses. Standard multiple imputation will be performed to assess the impact of missing data on the observed data.
- For statistical analyses of data to compare the effects of ACE-083 administered in the open-label extension versus the treatment received in the double-blind period of Part 2, the 90% confidence interval will be provided in place of the 95% confidence interval.

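### SAP 4.2 does not limit its 500 m walking-distance exclusion to Part 2, so any eligible Part 1 patient who walked further at screening would leave the primary analysis population for the secondary efficacy and MRI endpoints

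*SAP*

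**What the plan says.** **Eligibility.** Criterion 3 in Protocol 8.1, repeated in the synopsis, is split by part. Part 1 asks for "Six-minute walk distance (6MWD) of at least 150 meters (without a brace or walker") and gives no maximum. The upper bound, "and ≤ 500 meters (without a brace or walker"), stands under Part 2 alone.

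**Analysis set.** SAP 4.2 covers both parts with one definition: "Per Protocol Set: All patients enrolled/randomized in the study who have received at least one dose of study drug (includes placebo"), provided that there is no issue affecting how the efficacy or pharmacodynamic data can be interpreted. Its list of such issues includes "Patients whose Screening cumulative distance walked at 6 minutes is greater than 500 meters or less than 150 meters", with no part attached.

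**Role of the set.** The same section states: "Statistical analyses of efficacy and pharmacodynamics data will be performed on the Per Protocol Set (primary analysis population"); the Full Analysis Set is secondary. Again no part is named. The Part 1 analysis sections, SAP 4.7.2.1 (efficacy) and 4.8.2.1 (MRI and biomarkers), name no other population.

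**Protocol version of the set.** Protocol 14.1 has no walking-distance rule. It admits dosed patients "with no CSR-reportable protocol violations and at least one post-baseline MRI evaluation". SAP 5 records the change only as follows: "The “Per Protocol Set” definition was redefined to be what is listed in this document". It gives no reason and does not mention Part 1.

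**The concern.** A per-protocol exclusion should remove patients who departed from the rules that they were enrolled under. Here an entry limit for Part 2 is also written against patients enrolled under Part 1 criteria. For example, a Part 1 patient who walked 520 m at screening broke no walking-distance rule and would not be excluded on that ground by the protocol's own Per Protocol Set. Under SAP 4.2 the same patient leaves the population labelled primary.

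Part 1 has up to three cohorts of 6. Its secondary objectives (change in muscle volume, fat fraction, strength and motor function) are estimated by cohort, so each patient is 1/6, or 17%, of a cohort. At stake are the precision of those estimates and the range of walkers they describe.

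**Working it through.** **1. The texts side by side**

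| Screening 6MWD | Part 1 entry (Protocol 8.1) | Part 2 entry (Protocol 8.1) | Per Protocol Set (SAP 4.2) |
|---|---|---|---|
| below 150 m | not eligible | not eligible | excluded |
| 150 to 500 m | eligible | eligible | kept |
| above 500 m | eligible | not eligible | excluded |

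Only one cell conflicts: Part 1, above 500 m. The lower limit agrees in both parts.

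**2. The plan's own sample size**

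Part 1 has no formal calculation. For Part 2, SAP 4.1.1 gives a difference of 10%, an SD of 10%, a two-sided alpha of 0.10 and 90% power.

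- n per arm = 2 × (1.645 + 1.282)² × (10/10)² = 17.1, rounded up to 18, or 36 in total.
- Power of the t-test with 18 per arm, from the noncentral t distribution: 90.2%.
- Allowing for 10% dropout: 36 / 0.90 = 40.

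The stated 36 and 40 reproduce. Neither depends on how the exclusion is worded for Part 1.

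**3. What an exclusion would cost in Part 1**

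Inputs:
- 6 patients per cohort and 3 cohorts, 18 in total (Protocol 7.1, SAP Table 1).
- The Part 1 MRI model in SAP 4.8.2.1: an ANCOVA with baseline, cohort and their interaction. With three cohorts this has 3 intercepts and 3 slopes, so 6 mean parameters.
- Assumption: residual SD of 10 percentage points, borrowed from the Part 2 calculation. The documents give no SD for Part 1 MRI change.
- Approximation: standard error of a cohort mean = SD/√n, which ignores the extra term from adjusting for baseline.
- Unknown: the number of Part 1 patients above 500 m. A range is shown.

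Formula: 90% half-width = t(0.95, N − 6) × 10/√n, where n is the affected cohort's size and N the total. The other two cohorts stay at 6.

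| Excluded from one cohort | n | Residual df | t | Half-width (points) | Change |
|---|---|---|---|---|---|
| 0 | 6 | 12 | 1.782 | 7.3 | – |
| 1 | 5 | 11 | 1.796 | 8.0 | about +10% |
| 2 | 4 | 10 | 1.812 | 9.1 | about +25% |
| 3 | 3 | 9 | 1.833 | 10.6 | about +45% |

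The changes are 8.03/7.28 = 1.10, 9.06/7.28 = 1.25 (unrounded) and 10.58/7.28 = 1.45.

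The strength and timed-function models in SAP 4.7.2.1 add CMT type, so they have 7 parameters. With the same assumed SD, the half-widths for 0, 1 and 2 exclusions are 7.3, 8.1 and 9.2 points.

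**The case against.** **The list was drafted for Part 2.** One bullet names the Day 190 MRI, another refers to replaced patients (a rule that SAP 3.2 states for Part 2), and the exclusion list is to be completed before unblinding, although Part 1 is open-label. An omitted part label is a likely explanation, but the SAP does not say so. It marks parts elsewhere: the Full Analysis Set in the same section is split by part, and SAP 4.3 and 4.7.1.1 tag part-specific items. Other bullets, such as discontinuation before Day 43 or incomplete dosing, can apply to Part 1.

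**The plan already softens the effect.** The Full Analysis Set analysis keeps every dosed Part 1 patient, all individual data are listed, and exclusions are reviewed with reasons before lock. This stands as mitigation: no data disappear, and a difference between the sets would be visible. It does not remove the conflict. The review gives no basis for keeping a patient who meets a listed exclusion. Because Part 1 is open-label and its efficacy data are reviewed before Part 2 starts, a decision left to that review would be made with dose and outcome already known.

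**Only secondary estimation is touched.** This stands. Part 1's primary endpoint is safety, analysed on the Safety Set. The efficacy and MRI output is descriptive statistics and least-squares estimates with intervals, and no significance level is set for Part 1.

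**Selection bias between doses.** A reader might infer that removing strong walkers distorts the dose comparison. The documents give little support for this. The cut-off is measured before treatment and is the same in every cohort, so exclusion does not depend on response. The MRI model has no 6MWD term, so cohorts can differ in walking ability whether or not these patients are kept. What remains is smaller numbers and a narrower range of patients.

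**Conclusion.** The conflict is real on the text. It is conditional in effect and limited to the Part 1 efficacy and MRI analyses on the Per Protocol Set. If one or two patients in a cohort of 6 walked more than 500 m at screening, the cohort's approximate 90% half-width on MRI rises by about 10% or 25%, given an SD of 10%, a standard error of SD/√n and the pooled residual variance of the planned model.

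Three stronger readings are not supported:

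- That Part 1 patients are in fact lost. No section says that anyone in Part 1 exceeded 500 m. If nobody did, the results are the same under either wording.
- That the precision loss is +16% or +43%. Those figures come from a stand-alone interval for one cohort, t(0.95, n − 1)/√n, which gives 0.82, 0.95 and 1.18 SD for n = 6, 5 and 4. The SAP specifies one model across cohorts, with pooled residual variance.
- That the Part 2 dose decision is affected. Protocol 7.1 and 10.2 assign it to the Safety Review Team, and neither section ties that review to the Per Protocol Set.

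The point should be corrected because the rule, followed as written, excludes eligible patients and the correction costs almost nothing.

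**What to change.** In SAP 4.2, split the walking-distance bullet by part: exclude a screening 6MWD below 150 m in both parts, and above 500 m in Part 2 only. This matches Protocol 8.1. Defining the Per Protocol Set separately for each part would serve equally well.

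The cost is one line of SAP text before database lock. The Part 2 population and its figures (36 evaluable, 40 randomized) do not change, and in Part 1 no patient could be lost to the upper limit.
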